8.2 Reporting Adverse Events

Adverse events should be recorded on the appropriate CRF.

All **SAEs** should be reported to the sponsor within 24 hours of the Clinical Investigator becoming aware of the event fulfilling the criteria. The SAE form should be completed and e-mailed to the Project Manager/Monitor and the Joint Research Compliance Office. The minimum criteria required in reporting a SAE are the participant identifiers (trial number/date of birth), reporting source (name of Investigator), and why the adverse event is identifiable as serious.

Other important adverse events that should be reported to the sponsor within 24 hours of the Clinical Investigator becoming aware of the event, include

- allergic bronchospasm requiring intensive emergency treatment
- a seizure
- any adverse event that results in **discontinuation of the immunisation schedule**
- any adverse event that requires intervention to prevent a threat to life or death

SAE AND IMPORTANT AE NOTIFICATION

Within 24 hours of becoming aware of an SAE or Important AE, please enter onto the SAE CRF and indicate as serious and email the MRC CTU at UCL [contact] and the Imperial College London Joint Research Compliance Office at [contact]

SAE AND IMPORTANT AE NOTIFICATION

Faxes and emails should be acknowledged by the MRC CTU immediately on receipt. If the Clinical Investigator does not receive an acknowledgement they will assume that MRC CTU is not aware of the event and use an alternative method of notification.

The Principal Investigator will ensure that the SAE form is sent within 24 hours of an event. The Chief Investigator will assess whether the event qualifies in seriousness and relationship as a **Suspected Unexpected Serious Adverse Reaction (SUSAR)**. Fatal and life-threatening SUSARs must be reported to the MHRA within 7 days of day 0 which is defined as the day the sponsor became aware of the event. Relevant follow-up information should be sought and a further report completed as soon as possible and submitted within 8 additional days. SUSARs which do not result in death or a threat to life should be reported within 15 days of day 0. Ultimate responsibility for classification resides with the study Sponsor.

[figure not shown]
Investigators should notify the JRCO of all SAEs occurring from the time of randomisation until 30 days after the last protocol treatment administration. SARs and SUSARs must be notified to the JRCO until trial closure.

The MRC CTU Project Manager/Monitor will be responsible for coordination of the report review and filing with the JRCO at Imperial College London, and for ensuring the REC and MHRA are informed. From 01 May 2017 this responsibility will transfer to the study team at the Imperial CRF.

8.3 Pregnancy

Pregnancy is not an adverse event. However, it is a reportable event in a Phase I trial, and should be reported to the Chief Investigator within 24 hours of the Clinical Investigator becoming aware of the pregnancy by email, fax or phone.

All pregnancies will be followed up to collect information about the outcome which will be recorded in the clinical study report.

Figure 2: Safety Reporting Flowchart

9. WITHDRAWAL OF PARTICIPANTS

Withdrawal from the trial means stopping all further visits.

The reason(s) for withdrawal should be recorded on the Status CRF.

All participants are free to withdraw from the trial at any time, for any reason, without affecting their future medical care. An investigator may decide to withdraw a participant if the investigator deems that continuing might compromise participant wellbeing or interfere with the achievement of the trial's objectives.

Participants who are withdrawn due to an adverse event (AE) will be followed-up until the event has stabilised.

Withdrawn participants who have received any immunisations should be asked to undergo the procedures scheduled for the primary endpoint visit (Visit 10, week 22).

Policy for replacing withdrawals

Additional volunteers will be enrolled to replace early withdrawals or those who have discontinued their immunisations early, with the aim of having 24 subjects complete the study with no major protocol deviations. However, no more than 30 individuals in total will be exposed to the vaccine.

10. STATISTICAL CONSIDERATIONS

10.1 Method of Randomisation

Participants will be block-randomised centrally using a computer-generated algorithm with a back-up manual procedure. Randomisation will be stratified on the basis of gender.

10.2 Endpoints

10.2.1 Primary Endpoints

10.2.1.1 Safety

- Grade 3 or above local solicited adverse event (**Table 2**)
- Grade 3 or above systemic clinical and laboratory solicited adverse event (**Table 2**)
- Any grade of adverse event that results in a clinical decision to discontinue further immunisations
- Any grade of adverse event within 7 days of receiving intradermal and standard intramuscular vaccinations with or without electroporation

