The TDS-ID has been authorized for use as the means of DNA vaccine administration in a human clinical study of a DNA vaccine candidate for Venezuelan equine encephalitis virus. The study has enrolled 20 subjects in the TDS-ID arm of the study. The device was used to administer a series of three injections at DNA doses of up to 0.3 mg. Adverse responses reported in association with use of the device include acute discomfort / pain during EP application and minor cutaneous bleeding at the site of injection. Pinpoint eschar formation at the sites of needle formation has been commonly observed as well as transient injection site reactogenicity (erythema, induration, and/or soreness) of mild to moderate severity,

typically resolving within 24-72 hours following administration. Systemic adverse events reported during the study and judged to be possibly related to the study product and/or delivery device have been generally mild in severity and have included fatigue, headache, sore throat, and flushing. The findings are largely consistent with the adverse events observed with the TDS-IM device which has been utilized for the delivery of a wide range of DNA vaccines intended for use in oncology and infectious disease applications.

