The TDS-IM has been used as the means for administration in 20 completed or ongoing clinical studies totalling over 600 subjects. Adverse reactions associated with the use of the device include acute pain with localized muscle contractions in almost all subjects. Occasionally this is accompanied by mild, transient paresthesia. Mild, transient bleeding at the sites of electrode/needle penetration is commonly observed following removal of the device. Soreness, erythema, and/or induration of mild to moderate severity are commonly reported at the administration site. Transient vasovagal reactions, comprising mild dizziness, skin pallor, diaphoresis, light-headedness, and/or hypotension occurring immediately after device application, have been reported in approximately 1% of subjects. A more pronounced vasovagal reaction including a brief syncopic episode (of approximately 30 seconds duration) following device application was observed in one subject. Systemic adverse events reported during the studies and judged to be possibly related to the study product and/or delivery device have been generally mild to moderate in severity and include headache, fever, dizziness, malaise, fatigue, arthralgia, myalgia, influenza-like symptoms, and aphthous stomatitis. Transient elevation in serum creatinine phosphokinase of mild to moderate severity and judged to have at least a potential association with candidate administration have been reported in a small minority of subjects. Two subjects have reported a single instance of severe fatigue within 24 hours of dosing that was resolved by the following day.

To date, TDS-ID associated malfunctions observed in clinical trials to date have been limited to reports of device initiated interruption of the procedure prior to its completion. As described above, the device performs an impedance evaluation following electrode array insertion but prior to agent administration. In the event of an improper insertion of the electrodes (due to, for example, an inadequate depth of penetration into the skin or theoretically, distortion of the electrodes) is detected, the TDS-ID system will interrupt the administration procedure prior to the injection of the agent and notify the user. At that point, the device is withdrawn from the subject. The overall design of the TDS-ID system and the specific implementation of the impedance check are intended to minimize the occurrence of DNA administration without the subsequent application of EP.

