All volunteers will receive 3 immunisations of 2.0mg DNA IM and 0.6mg DNA ID and the immunisations will be administered with or without EP as described in table 1. In a supportive rabbit GLP toxicity study which was carried out with the same vaccine, the individual IM dose was 2mg, this was given for up to six administrations was shown to be well tolerated in rabbits (CR 525569) and lack of DNA persistence or distribution beyond the site of administration was demonstrated in rats (CR525574). Furthermore, a previous Phase I trial to use electroporation (EP) for the delivery of a DNA vaccine for HIV demonstrated increased immunogenicity in the absence of associated safety concerns [44] [62].

CN54gp140 Doses

We will give 1 immunisation of 50 μ g CN54gp140. In MucoVac 2 there was no significant impact on the magnitude of the responses after reducing the dose from 100 μ g to 20 μ g although this was in the presence of adjuvant.

2.2.4

Possible Next Steps

The following hypotheses will be explored with a view to informing the design of future trials both in terms of size and selection of methods:

- That each of the methods and combination regimens delivered with and without EP will be safe and acceptable
 - If any of the methods or regimens have unacceptable safety defined in terms of the proportion of participants that experience a grade 3 or above solicited adverse event or an event that leads to an investigator decision to discontinue immunisations, then there will be no further exploration of the route with the product/regimen.
- That immunisation via the combined IM+ID methods will elicit balanced immune responses.
- That EP will augment antibody responses to both ID and IM.

- That the greatest proportion of individuals will respond and make significantly greater antibody responses in group 3 (ID/EP + IM/EP) relative to the other groups. If EP is shown to impact upon the proportion of individuals making systemic IgG without compromising safety/tolerability, the strategy would be taken forward into future trials.

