7.4.3.2 Urine

- protein, ketones, blood, leukocyte esterase, and nitrites – by dipstick

A urine specimen will be sent to the laboratory if the level of protein, blood, leukocyte esterase or nitrites is considered clinically relevant.

Various local and systemic adverse events are known to be associated with licensed vaccines, and are referred to as '**solicited adverse events**'. These include disturbances in routine laboratory parameters, and are described in **table 2** below.

Information on solicited adverse events will be collected on the day of each immunisation (pre-immunisation, and at 10 and 60 minutes post-immunisation), at a safety call the day after each immunisation and for the following 7 days through a structured interview and examination according to the schedule.

In addition systemic laboratory adverse events will be collected through routine laboratory testing according to the schedule. These will be recorded on the appropriate CRF page.

Participants will also be asked to complete a diary card recording solicited adverse events that start within 7 days of each immunisation.

Table 2: Solicited Adverse Events

Type	Event
Local AEs (immunisation site)	Discomfort Redness Swelling (soft) Induration (hard) Blisters
Systemic Clinical AEs	Abnormally raised temperature Chills Myalgia/flu-like general muscle aches Malaise (excess fatigue) Headache Nausea Vomiting
Systemic Laboratory AEs	Abnormalities in: Creatinine, AST, ALT, alkaline phosphatase, total bilirubin, glucose Hb, total WCC, neutrophils, lymphocytes, platelets

The events will be **graded** according to the study specific toxicity table (see **Appendix 2**).

Relationship to study product, which is defined in **section 8**, will be recorded in the immunisation CRF but not on the diary card, on the assumption that any of these events starting within 7 days of an immunisation are at least possibly related. If the onset is beyond 7 days, the event will be recorded on the adverse event CRF and a relationship determined by the investigator reviewing the event.

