7.4.5 Non-solicited Adverse Events

Non-solicited AEs starting from the first vaccination until the final safety visit (Week 22) will be captured and reported on the adverse event CRF. When making a non-solicited AE enquiry, staff should ask a non-leading question such as 'how have you been feeling?'

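### The grade 3+ primary safety counts omit severe non-solicited reactions unless they lead to a decision to stop immunisation

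*Protocol*

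**What the plan says.** Protocol 10.2.1.1, repeated in 1.1.6 and SAP 3.1.1, has four primary safety items. Items 1 and 2 are "Grade 3 or above local solicited adverse event" and "Grade 3 or above systemic clinical and laboratory solicited adverse event", each tied to Table 2. Item 3 is "Any grade of adverse event that results in a clinical decision to discontinue further immunisations". Item 4 takes adverse events of every grade within 7 days of vaccination.

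The text introducing Table 2 in protocol 7.4 gives the origin of the list: "Various local and systemic adverse events are known to be associated with licensed vaccines, and are referred to as" solicited adverse events. The table names five local signs, seven systemic symptoms and the routine laboratory parameters.

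Protocol 2.2.4 defines unacceptable safety by the "proportion of participants that experience a grade 3 or above solicited adverse event or an event that leads to an investigator decision" to stop immunisations. The SAP Table 2 shell, titled as the primary safety outcome, covers items 1 to 3. Its event types are all solicited categories, and item 4 is not in its title.

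Protocol 2.2.2.3 reports device reactions that Table 2 does not name. For the intramuscular device these are mild paraesthesia, bleeding, bruising and vasovagal reactions, and in one subject "A more pronounced vasovagal reaction including a brief syncopic episode". For the intradermal device, "Pinpoint eschar formation at the sites of needle formation has been commonly observed". Appendix 2 grades immediate reactions (within 6 hours) under its heading for solicited reactions, with a grade 3 column, but Table 2 omits them. For non-solicited events, 7.4.5 says "staff should ask a non-leading question such as 'how have you been feeling".

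**The concern.** Where EP is applied is the only difference between the randomised arms, and comparing device safety with standard injection is the secondary objective. Earlier human use of the intradermal device is 20 people at DNA doses up to 0.3 mg. A severity count restricted to a list taken from licensed vaccines may be least complete for the reactions that could differ by arm. The risk is that the headline grade 3+ proportion, and the first limb of 2.2.4, show an arm as free of severe events when it was not.

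**Working it through.** **1. Where a grade 3+ event is counted**

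| Event | Items 1-2; first limb of 2.2.4 | Item 3; second limb of 2.2.4 | Item 4 (if within 7 days) | Elsewhere by grade |
|---|---|---|---|---|
| On Table 2 (e.g. severe pain, fatigue) | Yes | If it leads to stopping | Yes | SAP Tables 4-5 |
| Not on Table 2, leads to stopping | No | Yes | Yes | SAP Table 8; Table 3 if local |
| Not on Table 2, does not lead to stopping | No | No | Yes, grade ignored | SAP Table 8; Table 3 if local |

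The gap is the last row.

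**2. Does item 3 close it?** Protocol 6.1.5 makes stopping mandatory for a confirmed, related grade 3 or 4 event that has not resolved within 72 hours. The reported device reactions are mostly shorter: syncope about 30 seconds, paraesthesia seconds to minutes, local reactions typically 24 to 72 hours. An investigator may stop dosing sooner, but that is a judgement. A participant's own choice to stop is handled separately in 6.1.5 and is not an investigator decision.

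**3. Does item 4 close it?** It does not separate grades. Transient EP pain was reported by virtually all subjects with the intramuscular device, and all three arms receive EP. Item 4 is therefore likely to be near 100% in every arm. That is an inference; the documents give no expected figure.

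**4. Size.** Inputs: n = 8 per arm (SAP 2.2) and 95% Wilson intervals (SAP section 4), z = 1.96, z² = 3.8416.

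The limits are [p + z²/2n ± z√(p(1-p)/n + z²/4n²)] / (1 + z²/n).

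- 0/8: the upper limit reduces to z²/(n + z²) = 3.8416/11.8416 = 32.4%. SAP Table 3 prints 0-32%.
- 1/8: centre (0.125 + 0.2401)/1.4802 = 0.2467; half-width 1.96 × √(0.01367 + 0.01501)/1.4802 = 0.2242; limits 2.2% to 47.1%. SAP Table 3 prints 2-47%.
- All arms: 0/24 gives 0-14%; 1/24 = 4.2% gives 1-20%.

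The SAP intervals reproduce. Protocol Table 6 is headed n=8, but its rows match n=10 (0 events: 0-28%), so it is not used here.

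One uncounted participant therefore moves an arm from 0% (0-32%) to 12.5% (2-47%). Fisher's exact test for 0/8 against 1/8 gives p = 1.0, so the effect is on description, not on a test result.

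**The case against.** A reader might infer that severe EP reactions cannot count at all, or that 2.2.4 depends only on the solicited list. The documents do not support either. Item 3 and the second limb of 2.2.4 take any event that leads to a decision to stop. The 72-hour rule in 6.1.5 and the trial hold in 7.5 are not limited to Table 2. Severe tenderness and severe fatigue, both reported with the device, fit Table 2 as discomfort and malaise. Eschar might be graded under blistering or ulceration in Appendix 2. Section 2.2.4 sets no numeric threshold, so one event would not by itself pass or fail a route.

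A reader might also infer that such events would go unseen. That is not so either. Table 5 (footnote 7) has vital signs, site inspection and adverse event assessment at 10 and 60 minutes after each dose, and there is a next-day call. Local reactions within 7 days of Doses 1-3 are a secondary endpoint, shown by grade and arm in SAP Table 3. Other non-solicited events are in SAP Table 8 by grade and arm. SAP 4.5.1 also promises a description of grade 3 or above safety endpoints, which could include one that qualifies under item 4.

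Nor can a probability of a missed severe event be drawn from the protocol's rate of about 1% for vasovagal reactions. That rate is for mild reactions with the intramuscular device, which 16 participants receive with EP (1 - 0.99^16 = 14.9%). For the one pronounced reaction in just over 600 subjects, the same sum is 1 - (1 - 1/600)^16 = 2.6%.

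These objections narrow the point considerably. They do not put a brief, severe, non-listed event into the grade 3+ primary proportion.

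**Conclusion.** The point holds in a limited form. Items 1 and 2, the first limb of 2.2.4 and the SAP Table 2 shell omit non-solicited grade 3+ events; item 3 and the second limb recover only those that lead to a decision to stop. What remains is a severe, short-lived reaction outside Table 2, such as syncope after EP or a grade 3 immediate reaction as graded in Appendix 2. If one participant in an arm had such an event, the grade 3+ primary proportion would read 0/8 (0-32%) instead of 1/8 (2-47%).

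This assumes that Table 2, not Appendix 2, defines what is solicited, that the event does not lead to a decision to stop, and that the analysis has 8 per arm. How often such an event would occur cannot be estimated from the documents. The information is not lost, because SAP Tables 3 and 8 hold it. The fault is that the primary severity summary and the 2.2.4 rule do not use it. It is modest in size and worth correcting because correction is cheap.

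**What to change.** - Add to protocol 1.1.6 and 10.2.1.1, SAP 3.1.1 and the SAP Table 2 shell a line for any grade 3 or above adverse event, solicited or not, by arm. Show relatedness to vaccine or EP procedure as a breakdown, not as a condition for being counted; in an open-label trial this keeps attribution out of the primary count.
- Align the wording of 2.2.4 with that line.
- Restore item 4 to the SAP primary table.
- Reconcile protocol Table 2 with the solicited list in Appendix 2, immediate reactions in particular.

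The discontinuation rule in 6.1.5 and the hold in 7.5 are not touched.

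Cost: wording and one table row. Non-solicited events are already recorded, graded and assessed for relationship to vaccine (7.4.1, 7.4.5), so the count needs no new data. If attribution to the EP procedure was not recorded separately, show relationship to vaccine alone. The grade 3+ figure may be slightly less favourable and may include some unrelated events.

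Adding device reactions to the solicited list and diary card is optional. Under protocol 8.1, solicited events starting within 7 days are automatically classed as adverse reactions, so new terms would change how causality is assigned.

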10.2.1.2 Immunogenicity

- The magnitude of antigen specific systemic IgG antibody binding responses (µg/ml) 2 weeks after the final vaccination.

10.2.2 Secondary Endpoints

10.2.2.1 Safety

- Any grade of adverse event, local to the ID and IM injection sites, that starts within 7 days after Doses 1-3.

10.2.3 Exploratory immunogenicity endpoints

- Frequency and magnitude of HIV-gp140 specific B-cell-mediated responses in the systemic compartment measured by B-cell ELISPOT
- The magnitude of vaccine specific systemic T cell responses by T cell ELISpot assay
- The magnitude of antigen specific systemic IgA antibody responses (ug/ml)
- Frequency, titre and avidity of serum binding antibodies to other HIV Env antigens (alternative clades) by ELISA or other assays.
- Mapping of serum binding antibodies using Env subunit constructs (e.g., V2 scaffolds and hotspots) by ELISA.
- Frequency and magnitude of mucosal IgG and IgA antibody responses to CN54gp140 measured four weeks after the final immunisation.
- Frequency and titre of serum neutralising antibodies to homologous virus, and, if warranted a wider panel of viruses representing different clades.
- Frequency and magnitude of HIV-specific T-cell mediated responses measured by T-cell CFSE, and ICS (Intracellular Cytokine Staining).
- Frequency and magnitude of T-cell chemokine and cytokine release following ex-vivo antigen stimulation quantified by Luminex.
- Isolation and characterization of Env-specific monoclonal antibodies (IgG) from memory B cells in the systemic compartments (dependent upon elicited specific memory B-cell numbers).
- Characterisation of non-neutralising antibody function using ADCC/ADCVI, viral capture and aggregation assays.
- Epitope mapping of B- and T-cell responses.

10.2.4 Exploratory tolerability endpoints

- Pain scores at 0, 10 and 30 minutes following vaccination with EP

10.3 Sample Size

It is not the remit of this Phase I trial to recruit a sufficient number of participants to be statistically confident about the differences between groups. By the end of this study 8 participants will have been exposed to each schedule in groups 1, 2, and 3 and this provides confidence around the response/event proportions of 0–60% in table 6.

Table 6: Sample Size

Number of "responders"	Proportion if n=8	95% confidence interval¹
0	0%	0 – 28%
1	10%	2 – 40%
2	20%	6 – 51%
3	30%	11 – 60%
4	40%	17 – 69%
5	50%	24 – 76%
6	60%	31 – 83%

¹ Wilson interval (suitable for small sample sizes)

It is difficult to give an estimate of the power of group comparisons using quantitative antibody titre outcomes at this stage as this is dependent on the number of responders.

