2.1. Randomisation

Participants will be block-randomised using a computer-generated algorithm with a back-up manual procedure and randomisation will be stratified on the basis of gender. The randomisation lists are generated and checked by the trial statistician, and stored securely in the trial database.

Participants are randomised 1:1:1 to ID/EP, IM/EP or ID/IM/EP. Randomisation is unblinded.

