3.3.2. Tolerability

- Pain scores at 0, 10 and 30 minutes following vaccination with EP

4. Statistical Analyses

Analyses of safety and tolerability endpoints for randomized participants will be performed at the MRC CTU at UCL. Immunogenicity data are not held at the CTU, and will be analysed elsewhere.

Adverse events and vaccine responses will be described as frequencies with 95% confidence intervals. Confidence intervals will be calculated using Wilson intervals, suitable for small sample sizes (table 3).

Table 3. Wilson intervals

Number of events	N=8		N=7		N=6		N=5	
	%	95% CI						
0	0%	0,32%	0%	0,35%	0%	0,39%	0%	0,43%
1	13%	2,47%	14%	3,51%	17%	3,56%	20%	4,62%
2	25%	7,59%	29%	8,64%	33%	10,70%	40%	12,77%
3	38%	14,69%	43%	16,75%	50%	19,81%	60%	23,88%
4	50%	22,78%	57%	25,84%	67%	30,90%	80%	38,96%
5	63%	31,86%	71%	36,92%	83%	44,97%	100%	57,100%
6	75%	41,93%	86%	49,97%	100%	61,100%		
7	87%	53,98%	100%	65,100%				
8	100%	68,100%						

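### Protocol Table 6, the only sample-size justification, is headed n=8 but prints proportions and Wilson intervals for n=10

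*Protocol*

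**What the plan says.** Protocol section 10.3 disclaims any formal power for group comparisons and gives none for the antibody outcome: "It is difficult to give an estimate of the power of group comparisons using quantitative antibody titre outcomes at this stage". The quantitative case for the group size is therefore one of precision. The section says that "By the end of this study 8 participants will have been exposed to each schedule in groups 1, 2, and 3" and that "this provides confidence around the response/event proportions of 0–60% in table 6". Table 6 then lists 0 to 6 responders, a column headed "Proportion if n=8", and a column of 95% intervals that a footnote identifies as Wilson intervals.

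Eight per group is the figure used throughout. Table 1 in both documents shows N=8 in each of the three groups, SAP section 2.2 repeats 8 per method of delivery, and SAP section 2.1 gives equal allocation: "Participants are randomised 1:1:1 to ID/EP, IM/EP or ID/IM/EP". SAP section 4 also specifies Wilson intervals, and its Table 3 tabulates them for N = 8, 7, 6 and 5.

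**The concern.** One participant in 8 is 12.5%, yet Table 6 shows 10%. The printed proportions rise by exactly 10 points per responder, which happens only with a denominator of 10. If the intervals come from the same denominator, the table describes a larger group than the trial will have.

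This matters because section 10.3 offers no other calculation. Protocol section 2.2.4 also says that the proportion of participants with a grade 3 or higher solicited event, or with an event leading to discontinuation, will bear on whether a method is explored further, and that the proportion making systemic IgG will bear on whether electroporation is taken forward. A reader using Table 6 to judge how well 8 per arm can estimate those proportions is given the wrong limits.

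**Working it through.** **Inputs.** Group size 8 (Protocol 10.3, Table 1; SAP 2.2). Method: two-sided 95% Wilson score interval (footnote to Table 6; SAP section 4). z = 1.96, z² = 3.84.

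**Formula.** For x responders out of n, with p = x/n:

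limits = [p + z²/(2n) ± z·√(p(1−p)/n + z²/(4n²))] / (1 + z²/n)

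**Reproducing the printed figures (n=10).**
- 0 responders: the upper limit reduces to z²/(n + z²) = 3.84/13.84 = 27.8%. Table 6 prints 28%.
- 4 responders, p = 0.4: centre = (0.4 + 0.192)/1.384 = 0.428; half-width = 1.96·√(0.024 + 0.0096)/1.384 = 0.260; interval 16.8 to 68.7%. Table 6 prints 17 to 69%.

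**The same rows at n=8.**
- 0 responders: upper limit 3.84/11.84 = 32.4%.
- 4 responders, p = 0.5: centre 0.5; half-width = 1.96·√(0.03125 + 0.0150)/1.480 = 0.285; interval 21.5 to 78.5%.

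**All rows (percent).**

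| Responders | Table 6 as printed | Wilson, n=10 | Wilson, n=8 | SAP Table 3, N=8 |
|---|---|---|---|---|
| 0 | 0 (0–28) | 0 (0–27.8) | 0 (0–32.4) | 0 (0–32) |
| 1 | 10 (2–40) | 10 (1.8–40.4) | 12.5 (2.2–47.1) | 13 (2–47) |
| 2 | 20 (6–51) | 20 (5.7–51.0) | 25 (7.1–59.1) | 25 (7–59) |
| 3 | 30 (11–60) | 30 (10.8–60.3) | 37.5 (13.7–69.4) | 38 (14–69) |
| 4 | 40 (17–69) | 40 (16.8–68.7) | 50 (21.5–78.5) | 50 (22–78) |
| 5 | 50 (24–76) | 50 (23.7–76.3) | 62.5 (30.6–86.3) | 63 (31–86) |
| 6 | 60 (31–83) | 60 (31.3–83.2) | 75 (40.9–92.9) | 75 (41–93) |

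Every printed row equals the n=10 column after rounding. No printed interval equals the n=8 column, and only the 0% in the first row has the right proportion.

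**Could another method at n=8 explain the table?** Continuity-corrected Wilson, Clopper-Pearson, Jeffreys, Agresti-Coull and 90% Wilson intervals at n=8 were tried, as was the Wilson formula at n=8 applied to the printed proportions. None gives Table 6. Over n = 6 to 15, the plain 95% Wilson interval fits only n=10, where the largest deviation is 0.42 points (rounding). At n=8 it is 10.3 points, at n=9 5.1 and at n=11 4.4.

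**Size of the discrepancy.**
- Upper limits, SAP Table 3 minus Table 6: 4, 7, 8, 9, 9, 10 and 10 points for 0 to 6 responders.
- Lower limits, same order: 0, 0, 1, 3, 5, 7 and 10 points.
- Interval width, n=8 against n=10: 32.4 v 27.8, 44.8 v 38.6, 51.9 v 45.3, 55.7 v 49.5, 57.0 v 51.9, 55.7 v 52.7 and 51.9 v 51.9. The n=8 interval is 3.0 to 6.6 points wider for 0 to 5 responders and equally wide for 6.
- At a fixed proportion n=8 is wider: at 50%, 21.5–78.5 (57.0 points) against 23.7–76.3 (52.6 from these rounded limits).

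**The case against.** The strongest reply is that nothing turns on the table. The trial disclaims powered comparisons, and Protocol section 2.2.1 calls the immunology primarily descriptive. Eight per group was not derived from a target interval width. The safety hold in section 7.5 is a count of participants, and section 2.2.4 sets no numerical threshold. The SAP already holds the correct intervals, so no reported result would change. All of this stands, and it limits the harm; it does not make the table right.

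A second reply is that the loss of precision is partial. By responder count it applies to 0 to 5 responders; at 6 the width is the same and only the location is wrong. The gaps in the upper limits also mix a shift in the estimate with a loss of precision, and for 2 or more responders the printed lower limits are too low as well, which understates rather than flatters a response rate. This too is correct, and the size of the error should be described accordingly.

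A third possibility is that 10 per group reflects the cap of 30 exposed participants in Protocol section 9. That does not work. The cap allows for replacements, and the aim stated there is 24 completers. Replacements are defined as non-randomised in section 10.4.1, and their safety outcomes are reported separately under section 10.4.4, so they do not raise the randomised safety denominator to 10 per arm. They may enter the protocol's per-protocol population, but in place of participants who did not complete. The column heading and the sentence above the table both say 8.

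**Conclusion.** The concern holds. All seven intervals and six of the seven proportions in Protocol Table 6 are wrong for the stated group size; they belong to 10 per arm (3 × 10 = 30), not 8 per arm (3 × 8 = 24). The range of 0–60% in the text should be 0–75% for 0 to 6 of 8. The most consequential row for safety is zero events: the upper two-sided 95% Wilson limit is 32%, not 28%. The protocol also contradicts SAP Table 3, which is correct.

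The conclusion rests only on the stated n of 8, the stated Wilson method and the 95% level. The practical effect is modest: 3.0 to 6.6 points of interval width for 0 to 5 responders, upper limits 4 to 10 points too low, and no effect on the planned analysis. It should be corrected because it is the protocol's only quantitative justification of its size.

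**What to change.** In Protocol section 10.3:

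- Replace Table 6 with the n=8 Wilson values for 0/8 to 8/8. These are the N=8 column of SAP Table 3, with the last two rows 7/8 (53–98%) and 8/8 (68–100%). Print 7/8 as 87.5% or 88%: the SAP shows 87%, although it rounds 12.5, 37.5 and 62.5 up. The SAP entry can be aligned at the same time.
- Change the range in the sentence above the table to 0–100% if all nine rows are shown, or to 0–75% if the table stops at 6 responders.
- Add that with zero events in an arm of 8 the upper two-sided 95% Wilson limit is 32%. Name the method, because the limit depends on it: the Clopper-Pearson upper limit for 0/8 is 36.9%.

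The cost is a text correction. Design, conduct and analysis are unchanged; the only downside is that the stated precision becomes slightly less favourable.
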